### **7.3.7. Time to Qualification for Retreatment**

These analyses will be based on ITT 1, 2 and 3 populations.

The number and percentage of event of interest will be presented by visit. Time to event data will be summarized using the descriptive statistics below and listed.

- The number of events and censored cases.
- Median survival time with the associated 95% CI.
- 25% and 75% survival time.

Survival analyses will be conducted using a Kaplan-Meier method. To graphically compare the survival functions between 400 units and 240 units, the analysis will be conducted based on ITT 1 population whereas the analyses will be based on ITT 2 and 3 populations to assess the survival time by treatment cycle. Participants who are withdrawn from this study before the events are censored at the withdrawal date. All other participants who do not experience the event and is not withdrawn from study are censored at the Last Observed Visit at the interim analyses or the final analyses.

Survival function estimates will be summarized (survival probabilities and the number of participants at risk per time to event, and median in survival time) based on Kaplan Meier method. Kaplan Meier plots will be presented.

Note that the retreatment is not allowed within 83 days from the previous treatment. Therefore, this event will not occur before 83 days later after the treatment/re-treatment.

CONFIDENTIAL

207660

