**10.2. Appendix 2: Schedule of Activities**

**10.2.1. Protocol Defined Schedule of Events**

	Screening a	Blind phase 1) If a participant meets the eligibility at V5/ QRV, the participant will move forward to the open- label phase						Open-label phase If a participant meets the eligibility at V5/QRV, the participant will move forward to the next treatment phase						Completion visit
		Part 1					Eligibility evaluation b	Part 2/Part 3/ Part 4				Eligibility evaluation b		
Visit	SV	V1 (Day 1)	V2	V3	V4	V5 c (Eligibility evaluation)	QRV	V1	V2	V3	V4	V5 d (Eligibility evaluation)	QRV	Final Visit
Time from initial injection (Day 1) (Weeks)	—	0	2	4	6	12	Allowable Week 16 to 36 e	—	—	—	—	—	Allowable Week 24 to 36 e	48/ Withdrawal
Time from injection day in each treatment phase (Weeks)	—	0	2	4	6	12	16/ 20/ 24/ 28/ 32/ 36	0	2	4	6	12	16/ 20/ 24	-
Acceptable visit windows (days)		—	±4	±4	±4	+4 f	±14 g	(+4) v	±4	±4	±4	+4 f	±14 g	±4
Written informed consent	X h													
Randomization		X i												
Injections		X						X						
Evaluation of eligibility						X	X					X	X	
Inclusion/exclusion criteria j	X	X i												
Participant demography	X													
MAS k	X	X i	X	X	X	X	X	X i,t	X	X	X	X	X	X
NRS l		X i	X	X	X	X		X i,t	X	X	X	X		(X) r
DAS		X i	X	X	X	X		X i,t	X	X	X	X		(X) r
CGI by a investigator			X	X	X	X			X	X	X	X		(X) r
CGI by a patient			X	X	X	X			X	X	X	X		(X) r
Time to patient-reported onset of spasticity symptom relief			X						X					
Patient-reported benefit of injection				X	X	X				X	X	X		(X) r
Physical examination	X													

CONFIDENTIAL

207660

	Screening a	Blind phase 1) If a participant meets the eligibility at V5/ QRV, the participant will move forward to the open- label phase					Eligibility evaluation b	Open-label phase If a participant meets the eligibility at V5/QRV, the participant will move forward to the next treatment phase					Completion visit	
		Part 1						Part 2/Part 3/ Part 4						Eligibility evaluation b
Visit	SV	V1 (Day 1)	V2	V3	V4	V5 c (Eligibility evaluation)	QRV	V1	V2	V3	V4	V5 d (Eligibility evaluation)	QRV	Final Visit
(complete version)														

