Physical examination (simplified version)		X 				X		X 1,t				X		X
Medical history	X	X 												
Vital signs m	X	X 				X		X 1,t				X		X
Height	X													
Body weight	X					X u	X u					X u	X u	
Pulmonary function test	X	X				X	X u					X	X u	X
Electrocardiogram	X					X u	X u					X u	X u	
Pregnancy test n	X	X 				X u	X u					X s, u	X u	X
Laboratory test o	X					X						X		X
Adverse events p	X	X	X	X	X	X	X	X	X	X	X	X	X	X
Concomitant medications/therapies	X	X 	X	X	X	X	X	X	X	X	X	X	X	X
Testing for neutralising antibodies q	X					X								X

- Test items for screening must be performed from 4 weeks to 1 weeks before Day 1 visit (±3 days).
- Eligibility evaluation (Qualification for Retreatment Visit: QRV) will be performed at V5 as a starting point if a participant does not meet the criteria only. The evaluation is performed at a 4-week interval, V5 as a starting point, The QRV when a participant meets the criteria will be a same day as the injection in the next treatment period.
- If a participant is evaluated to meet the eligibility for the injection in the blind phase at V5, the participant will move forward to Part 2 in the open-label phase (Namely, V5 in Part 1 and V1 in Part 2 is a same day). If the participant does not meet the eligibility, QRV will be performed 4 weeks later, at V5 as a starting point.
- If a participant is evaluated to meet the eligibility at V5 in the open-label phase, the participant will move forward to the next treatment phase (V5 and V1 in the next treatment phase is a same day). If the participant does not meet the eligibility, QRV is performed 4 weeks later, V5 as a starting point. If V5 in each treatment phase is at Week 48 after initial injection, V5 will be considered to be completion visit (FV). However, for the testing items, pre-scheduled tests at

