## CONFIDENTIAL

207660

V5 and neutralizing antibody tests will be performed. If V5 in Parts 2 and 3 is performed at Week 36 or later, after completion of V5, completion visit will be performed at Week 48.

- e. QRV is allowable to perform from initial injection to Week 36. Eligibility evaluation (QRV) will not be performed after Week 36.
- f. V5 must be performed at least 84 days after V1.
- g. The acceptable visit windows will be -14 to +4 days if QRV is performed at Week 36.
- h. Must be performed earlier than any other procedures
- i. Must be performed before injection of the product
- j. For inclusion/exclusion criteria, the items to be observed are different between screening phase and Day 1. For details, refer to Protocol Section 6.1 and Section 6.2.
- k. For MAS evaluation, the items to be evaluated differ depending on the treatment phase. For details, refer to Protocol Section 9.1.1.1.
- l. MAS evaluation will be followed by NRS evaluation. For NRS evaluation, items to be evaluated differ. For details, refer to Protocol Section 9.1.1.2.
- m. Body temperature, heart rate, and blood pressure will be measured as vital signs.
- n. Women of childbearing potential will be only performed. Serum hCG pregnancy test must be performed at screening, and urine hCG pregnancy test after randomization. The tests can be performed beyond the protocol specifications if an investigator considers to be necessary.
- o. For laboratory test items, refer to Protocol Section 12.2. Attachment 2. Fasting is not required for blood collection.
- p. Adverse events and serious adverse events collection period will be from the initial injection day (Day 1) to completion visit (FV).
- q. Neutralizing antibody testing is performed 3 times in each participant. The first test will be performed in screening phase, the second is at V5 in the blind phase, and the third is at completion visit.
- r. A participant who withdraws the study before 12 weeks after last injection will be performed.
- s. Perform if V5 in each treatment phase is at Week 48 after initial injection
- t. Not necessary to perform doubly as V1 assessment if the same assessment is performed at V5 or QRV. If V1 assessment or retreatment cannot be performed on the same day as V5 or QRV, MAS assessment should be performed again on the day of visit for the V1 assessment.

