**10.6.3. Efficacy**

Time to Event Data
Time to Qualification for Retreatment

 
This time to event data will be derived based on the following formula:  <math display="block">\text{Time to Event (Days)} = \text{Date When a Participant Meets the Criteria for Retreatment} - \text{Study Treatment Start Date (Days)}</math> 
 
If a participant is withdrawn from this study, the participant will be regarded as censoring and censored date will be a withdrawal date.
 

Time to Patient Reported Onset of Spasticity Symptom Relief

 
This time to event data will be derived based on the following formula:  <math display="block">\text{Time to Event (Days)} = \text{Onset Date of the Spasticity Symptom Relief} - \text{Study Treatment Start Date (Days)}</math> 
 
 
If a participant is withdrawn from this study, the participant will be regarded as censoring and censored date will be a withdrawal date.

CONFIDENTIAL

207660

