Time to Qualification for Retreatment					
2.49.	ITT1	EFF_T8	Summary of Events in Which a Participant Meets the Criteria for Retreatment		SAC
2.50.	ITT1	EFF_T6	Summary of Time to Qualification for Retreatment		SAC

CONFIDENTIAL

207660

Efficacy: Tables					
No.	Population	IDSL / Example Shell	Title	Programming Notes	Deliverable
2.51.	ITT1	EFF_T7	Summary of Survival Analyses Results of Time to Qualification for Retreatment in Blind Phase	
 
Survival function estimates will be summarized
 
Two treatment arms (240 and 400U)
 
	SAC
2.52.	ITT2	EFF_T7	Summary of Survival Analyses Results of Time to Qualification for Retreatment in Open Label Phase (2nd Treatment)	
 
Survival function estimates will be summarized
 
	SAC
2.53.	ITT3	EFF_T7	Summary of Survival Analyses Results of Time to Qualification for Retreatment in Open Label Phase (3rd Treatment)	
 
Three treatment arms (240, 400 and 240 + 400U)
 
	SAC

CONFIDENTIAL

207660

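### Time to qualification for retreatment: cycle 2 and 3 participants stay in the risk set after eligibility evaluation has ended, so the proportion not yet qualified is overstated (exploratory endpoint, final analysis)

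*SAP*

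**What the plan says.** Section 7.3.7 plans Kaplan-Meier estimates for ITT1 (to compare the doses after the first injection) and for ITT2 and ITT3 (by treatment cycle). Withdrawal before the event censors at the withdrawal date. For the rest: "All other participants who do not experience the event and is not withdrawn from study are censored at the Last Observed Visit", at the interim or final analysis. The term is not defined.

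Section 10.6.3 takes the event date as "Date When a Participant Meets the Criteria for Retreatment" and counts days from the study treatment.

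The schedule in Appendix 2 (Section 10.2.1) sets the open-label qualification visits (QRV) at cycle Weeks 16, 20 and 24, with the calendar limit "Allowable Week 24 to 36". Footnote e adds: "Eligibility evaluation (QRV) will not be performed after Week 36". Follow-up continues. If Visit 5 (V5) of Part 2 or 3 falls at Week 36 or later, footnote d says that "after completion of V5, completion visit will be performed at Week 48".

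The affected displays are Tables 2.52 and 2.53 and Figures 2.54 and 2.55, all in the final analysis. The amended interim displays for this endpoint use ITT1 only.

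**The concern.** Kaplan-Meier estimation assumes that a participant counted as at risk could be seen to have the event at that time. Here the opportunity ends at Week 36 while follow-up runs to Week 48. In cycle 1 everyone starts at the same time and can be evaluated up to Week 36, so the later follow-up only adds a flat tail. In cycles 2 and 3 the time origin is a later injection. The end of evaluation then falls at a different cycle week for each participant, and for late injections before the first possible evaluation. These participants enlarge the denominators at cycle Weeks 12 to 24 but cannot contribute events.

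The SAP already applies this reasoning to cycle 4. The amendment table in Section 1.1 explains that ITT4 was removed from this analysis because participants treated four times were not assessed for retreatment. Second and third injections at Weeks 28 to 36 are in the same position but stay in ITT2 and ITT3.

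At stake are the cycle 2 and 3 curves and medians, which describe how long the effect of repeated injections lasts.

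**Working it through.** **Inputs from the SAP.** First evaluation in a cycle at Week 12, then every 4 weeks; none after calendar Week 36; final visit at Week 48; 120 randomized. Schedule check: the earliest second injection is at Week 12, and 12 + 24 = 36, which agrees with cycle Week 24 as the last open-label QRV.

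**Who can have the event.** With an injection at calendar Week t, evaluation is possible at cycle week w only if t + w ≤ 36. With the final visit as last observed visit, the plan censors at cycle week 48 − t.

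| Injection at Week | Evaluations possible (cycle weeks) | Censored under the plan (cycle week) |
|---|---|---|
| 12 | 12, 16, 20, 24 | 36 |
| 16 | 12, 16, 20 | 32 |
| 20 | 12, 16 | 28 |
| 24 | 12 | 24 |
| 28 / 32 / 36 | none | 20 / 16 / 12 |

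The third injection is at Week 24 at the earliest (12 + 12), so cycle 3 has one possible evaluation, for that group only.

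**Assumptions (not in the SAP).** Chance p of qualifying at cycle Week 12 and r at each later evaluation, equal for all participants and cycles; no withdrawals.

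**Cycle 3, p = 0.5, r = 0.4.** Expected third injections out of 120:
- Week 24: 120p² = 30
- Week 28: 120 × 2p(1−p)r = 24
- Week 32: 120 × [2p(1−p)(1−r)r + ((1−p)r)²] = 14.4 + 4.8 = 19.2
- Week 36: 120 × [2p(1−p)(1−r)²r + 2(1−p)²r²(1−r)] = 8.64 + 5.76 = 14.4

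The total is 87.6, of whom 30 can be evaluated. Expected events at cycle Week 12 are 30 × 0.5 = 15. The plan gives 1 − 15/87.6 = 0.829; censoring at the last evaluation gives 1 − 15/30 = 0.500, the assumed value.

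**Cycle 2, same rates.** Second injections up to Week 24: 60 + 24 + 14.4 + 8.64 = 107.04. At Weeks 28, 32 and 36: 5.18 + 3.11 + 1.87 = 10.16. Total 117.2.
- Week 12: events 107.04 × 0.5 = 53.52. Plan 1 − 53.52/117.2 = 0.543; last evaluation 1 − 53.52/107.04 = 0.500.
- Week 16: at risk 117.2 − 53.52 − 1.87 = 61.8, events 19.68, plan 0.543 × (1 − 19.68/61.8) = 0.370.
- Week 20: at risk 61.8 − 19.68 − 3.11 = 39.0, events 10.08, plan 0.275.
- Week 24: at risk 39.0 − 10.08 − 5.18 = 23.8, events 4.32, plan 0.225. Assumed value 0.5 × 0.6³ = 0.108.

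**Range, by the same steps.** Proportion not yet qualified, plan against assumed value (difference):

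| p / r | Cycle 3, Week 12 | Cycle 2, Week 12 | Cycle 2, Week 24 |
|---|---|---|---|
| 50% / 40% | 0.829 vs 0.500 (0.33) | 0.543 vs 0.500 (0.04) | 0.225 vs 0.108 (0.12) |
| 50% / 50% | 0.846 vs 0.500 (0.35) | 0.528 vs 0.500 (0.03) | 0.162 vs 0.062 (0.10) |
| 60% / 50% | 0.749 vs 0.400 (0.35) | 0.426 vs 0.400 (0.03) | 0.117 vs 0.050 (0.07) |
| 80% / 40% | 0.434 vs 0.200 (0.23) | 0.227 vs 0.200 (0.03) | 0.071 vs 0.043 (0.03) |
| 80% / 50% | 0.455 vs 0.200 (0.26) | 0.218 vs 0.200 (0.02) | 0.046 vs 0.025 (0.02) |

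**If the undefined visit means the last V5 or QRV within the cycle.** Cycle 3 is unchanged. In cycle 2 with 50%/40%, Week 12 stays at 0.543 and Week 24 falls to 0.117 against 0.108.

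**The case against.** **Is evaluation really impossible after Week 36?** The SAP does not say so outright. Footnote e names the QRV, while the schedule also labels V5 as an eligibility evaluation and gives it no calendar limit. The protocol may settle whether the criteria are scored at a V5 after Week 36. The likelier reading is that they are not used: footnote d sends such participants to the completion visit, and the same schedule column covers Part 4, whose participants the amendment describes as not assessed. If the criteria are in fact scored at a late V5, the bias is smaller.

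**How much depends on this endpoint?** Little. It is exploratory, no hypothesis is tested, the dose comparison uses ITT1, and numbers at risk and censored will be shown. This limits the weight of the point but does not make the planned curves right.

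**Is the proposed censoring unbiased?** Not in cycle 3. The match to the assumed values above follows from giving everyone the same chances. The only evaluable cycle 3 participants are those who qualified at Week 12 in both earlier cycles. In a simulation with chances varying between participants (beta-distributed, means 0.6 and 0.5, precision 2, the two chances tied within a participant), cycle 3 at Week 12 was 0.51 under the plan and 0.20 with last-evaluation censoring, against a true 0.27. The error is smaller but runs the other way. This objection stands and shapes the fix.

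**Stronger readings a reader might infer.** One is that the cycle 3 median will come out as not reached. That happens at 50-60% qualifying at Week 12; at 80% it is Week 12 either way. Another comes from Section 10.6.3, which says "If a participant is withdrawn from this study, the participant will be regarded as censoring and censored date will be a withdrawal date" without the condition in 7.3.7 that withdrawal precedes the event. One might conclude that observed events would be deleted. Section 7.3.7 states the condition and resolves the mismatch, so this is only a wording clean-up.

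**Conclusion.** The concern holds as a should-fix point on an exploratory endpoint in the final analysis. As written, the rule keeps cycle 2 and 3 participants at risk after they can be found to qualify. At cycle Week 12 the direction is certain if evaluation ends at Week 36, because anyone not evaluated is counted as not qualified.

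Over 50-80% qualifying at Week 12 and 40-50% at each later visit, with equal rates in all cycles and no withdrawals, the overstatement is about 0.23-0.35 in cycle 3 at Week 12 (0.26 or more except at 80%/40%). In cycle 2 it is about 0.02-0.04 at Week 12 and 0.02-0.12 at Week 24. These sizes rest on assumed rates, and the Week 24 figures also on reading the last observed visit as the final visit.

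Cycle 1 to Week 36, the dose comparison over that period and the primary endpoint are unaffected. Curves that appear to show longer duration with repeat dosing could arise from the censoring rule alone, but no between-cycle test is planned and the SAP does not claim such a finding.

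**What to change.** In Section 7.3.7, replace the undefined last observed visit: censor participants without the event at their last eligibility evaluation (V5 or QRV) on or before Week 36 in that cycle. Remove participants with no such evaluation from the risk set before cycle Week 12, and report their number by cycle. State how a V5 after Week 36 is treated.

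For cycle 3, report the proportion qualifying at Week 12 among evaluable participants, described as applying to those who requalified at Week 12 in both earlier cycles. Alternatively, drop Table 2.53 and Figure 2.55, as was done for ITT4.

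As a clean-up, add the before-the-event condition to the withdrawal rule for this endpoint in Section 10.6.3.

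The cost is a few sentences and one derived censoring variable; the clinical schedule does not change. The downside is fewer participants at risk (30 of 87.6 expected in cycle 3 at 50%/40%) and a cycle 3 estimate that leans towards shorter duration, because it describes fast requalifiers.

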## 8. SAFETY ANALYSES

The safety analyses will be based on the Safety 1, 2, 3 and 4 populations, unless otherwise specified.

### 8.1. Adverse Events Analyses

Adverse events analyses including the analysis of adverse events (AEs), Serious (SAEs) and other significant AEs will be based on GSK Core Data Standards. The details of the planned displays are provided in [Appendix 12: List of Data Displays](#).

Adverse events that occurred in the overall study period, blinded period and open-label period will be summarized for each treatment group. The treatment group is based on dose actually given in blind period. For the blinded period, 2 patterns of analyses on adverse events will be performed, one is on adverse events that occurred between the initial dose and the first dose in the open-label period (or at the completion of study if no dose is given in the open-label period or at the study withdrawal), and another one is on adverse events that occurred within 84 days from the initial dose.

Overall study period (Treatment Emergent AEs)

Blind phase

1. AEs occurred between the initial dose and the first dose in the open-label period (or at the completion of study if no dose is given in the open-label period or at the study withdrawal)
2. AEs occurred within 84 days from the initial dose

Open-label phase

- 3.01. AEs occurred during 2nd treatment cycle.
- 3.02. AEs occurred during 3rd treatment cycle.
- 3.03. AEs occurred during 4th treatment cycle.

The number and percentages of participants who experience at least one AE will be presented for each category of AE listed as below by treatment group.

- All Treatment Emergent AEs (by SOC and PT, by SOC, PT and Maximum Intensity)
- Common AEs ( $\geq 3\%$ ) (by overall frequency)
- Drug Related AEs (by SOC and PT, by SOC, PT and Maximum Intensity)
- Non-Fatal Serious AEs
- Drug Related Non-Fatal Serious AEs
- AEs Leading to Withdrawal from Study (by SOC and PT)
- Most Common Serious Drug Related AEs (by overall frequency)
- Most Common Non-Serious Drug Related AEs (by overall frequency)
- Common ( $\geq 5\%$ ) Non-Serious AEs (by SOC and PT)
  - Number of Participant and Occurrences will be presented.

